### 5.3 Changes in the Conduct of the Study or Planned Analyses

#### 5.3.1 Changes in the Conduct of the Study

Prior to database lock, there were no changes in study conduct.

#### 5.3.2 Changes to Analyses Prior to Database Lock

Cross table for overall lip fullness responders between subjects and Evaluating Investigators will not be provided.

## 6. Data Handling and Analysis Conventions

### 6.1 Analysis Days

Analysis day for effectiveness, ISR, and AE are defined as follows:

**Table 6-1 Analysis Day Definitions**

Term	Description
Analysis day: Effectiveness Day	VOLBELLA Group Relative to the last treatment date (either the initial treatment, if no touch-up is performed,

Term	Description
	
or the touch-up treatment)
 
If analysis date <math>\geq</math> last treatment date:
 
 
• Effectiveness Day = analysis date – last treatment date + 1
 
• Effectiveness Day 1 = last treatment date
 
 
If analysis date <math><</math> last treatment date:
 
 
• Effectiveness Day = analysis date – last treatment date
 
• Effectiveness Day -1 = day before last treatment date
 
 
Control group before receiving treatment                      Relative to the randomization date
 
If analysis date <math>\geq</math> randomization date:
 
 
• Effectiveness Day = analysis date –randomization date +1
 
• Effectiveness Day 1 = randomization date
 
 
If analysis date <math><</math> randomization date:
 
 
• Effectiveness Day = analysis date –randomization date
 
• Effectiveness Day -1 = day before randomization date
 
 
Control group after receiving treatment                      Relative to the last treatment date (either the initial treatment, if no touch-up is performed, or the touch-up treatment)
 
If analysis date <math>\geq</math> last treatment date:
 
 
• Effectiveness Day = analysis date – last treatment date + 1
 
• Effectiveness Day 1 = last treatment date
 


Analysis day                      Safety Day
	
VOLBELLA Group                      Relative to the immediate prior treatment date (initial or touch-up)
 
If analysis date <math>\geq</math> initial treatment date:
 
 
• Safety Day = analysis date – immediate prior treatment date + 1
 
• Safety Day 1 = immediate prior treatment date
 
 
If analysis date <math><</math> initial treatment date:
 
 
• Safety Day = analysis date – immediate prior treatment date
 
• Safety Day -1 = day before immediate prior treatment date
 
 
Control group before receiving treatment                      Relative to the randomization date
 
If analysis date <math>\geq</math> randomization date:
 
 
• Safety Day = analysis date –randomization date +1
 
• Safety Day 1 = randomization date
 
 
If analysis date <math><</math> randomization date:
 
 
• Safety Day = analysis date –randomization date
 
• Safety Day -1 = day before randomization date
 
 
Treated Control after receiving treatment                      Relative to the immediate prior treatment date (initial or touch-up)
 
If analysis date <math>\geq</math> initial treatment date:
 
 
• Safety Day = analysis date – immediate prior treatment date + 1
 
• Safety Day 1 = immediate prior treatment date
 

### 6.1.1 Missing/Incomplete Treatment End Date

Not applicable.

## 6.2 Analysis Visit Windows

### 6.2.1 Effectiveness

The analysis visit windows for effectiveness endpoints are defined as follows:

**Table 6-2 Effectiveness Analysis Visit Definitions for Treatment Group**

Analysis Visit	Target Day of the Visit	Analysis Visit Window
Screening a	N/A	Screening visit
Baseline	N/A	Randomization/Initial treatment visit
Touch-up treatment b	Day 30 After Initial Treatment	Day 30 after initial treatment visit
Last treatment c	Day 1	Day 1
Month 1	Day 31	Days [2, 61]
Month 3	Day 91	Days [62, 136]
Month 6	Day 181	>=Day 137

a Subjects may have screening and randomization on the same day. In such cases, only randomization visit is relevant.

b Not all subjects will receive touch-up treatment.

c Initial treatment if touch-up is not performed, otherwise touch-up treatment

**Table 6-3 Effectiveness Analysis Visit Definitions for Control Group during Control Period**

Analysis Visit	Target Day of the Visit	Analysis Visit Window
Screening a	N/A	Screening visit
Baseline	Day 1	Randomization visit
Month 1	Day 31	Days [2, 61]
Month 3	Day 91	From Day 62 to study exit day if the subject didn't receive optional treatment, or to the day of optional treatment if the subject received optional treatment  The assessments before the optional treatment on that day will be accounted for Month 3 visit.

**Table 6-4 Effectiveness Analysis Visit Definitions for Control Group during Treatment Period**

Analysis Visit	Target Day of the Visit	Analysis Visit Window
Baseline	N/A	Randomization visit
Initial treatment a	N/A	N/A
Touch-up treatment b	Day 30 After Initial Treatment	Day 30 after initial treatment visit
Last treatment c	Day 1	Day 1
Month 1	Day 31	Days [2, 61]

Month 3	Day 91	Days [62, 136]
Month 6	Day 181	>=Day 137

aInitial treatment is at Month 3 visit.

bNot all subjects will receive touch-up treatment.

cInitial treatment if touch-up is not performed, otherwise touch-up treatment.

If there are multiple visits occurring within a single visit window with relevant data, the visit closest to the target day listed above will be used in the analysis of the corresponding visit windows regardless of scheduled or unscheduled visit. If two visits are equal distant to the target day and are the same type of visit, then the later visit will be used.

## 6.2.2 Safety

No analysis visit windows are required for TEAEs and ISRs.

## 6.3 Missing/Incomplete Date Conventions

### 6.3.1 Missing/Incomplete AE Start Date

Imputation of dates with missing day and/or month is only applied to TEAEs. If adequate information is available, no imputation is needed. TEAE start dates with missing day or month will be imputed as following:

- If day and month are missing but year is available, then the imputed day and month will be 01 Jan or the initial treatment date if they have the same year, whichever is later (because TEAE onset is not expected prior to administration of study treatment)
- If day is missing but the month and year are available, then the imputed day will be the first day of the month or the initial treatment date if they have the same month and year, whichever is later

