9.1.3 Treatment Regimen Adjustment

Up to 2 treatment sessions 30 days apart are allowed. The Treating Investigator will determine the appropriate volume of VOLBELLA with Lidocaine to inject at the initial and touch-up treatments based on his/her clinical experience and the randomization assignment, but the maximum volume is not to exceed 4.0 mL for initial and touch-up treatments combined.

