**Table 5-19 AE Summaries**

Endpoint	Description	Timing	Methodology
Overall summary	Treatment-emergent AEs (TEAEs) 
 
• Treatment-related TEAEs               
 
○ At injection site
 
○ Not at injection site
 
 
 
• All Serious AEs (SAEs)               
 
○ Treatment-related SAE                   
 
▪ At injection site
 
▪ Not at injection site
 
 
 
 
 
• Discontinued due to TEAE
 
• Deaths
 
	TP	Categorical counts, Event descriptives
TEAEs	
 
• Overall summary and by SOC, PT, and severity
 
	TP	Categorical counts, Event descriptives
Treatment-related	
 
• Overall summary and by SOC, PT, and severity
 
	TP	Categorical counts,

Endpoint	Description	Timing	Methodology
TEAEs	severity 
 
Overall summary by duration, time to onset, outcome, and treatment required
 
		Event descriptives
SAEs	Overall summary and by PT	TP	Listing
AEs leading to discontinuation	Overall summary and by PT	TP	Listing

Note: SOCs will be sorted alphabetically; PTs will be sorted in descending frequency in the treatment group. AEs for control group after optional treatment are summarized.

Time to onset for TEAEs will be computed as

$$\text{AE start date} - \text{reference date} + 1,$$

where the reference date is initial treatment date for TEAEs occurring on or after initial treatment but before touch-up treatment, and the reference date is touch-up treatment date for TEAEs occurring on or after touch-up treatment.

Duration for TEAEs will be computed as AE end date – AE start date + 1.

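### The partial-onset rule ignores the touch-up date, so an adverse event that began after a touch-up in the same calendar month, day unknown, is timed from the wrong injection

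*SAP*

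**What the plan says.** SAP 6.3.1 has two bullets for incomplete onset dates of treatment-emergent events.

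- Day missing: "the imputed day will be the first day of the month or the initial treatment date if they have the same month and year". The later of the two dates applies.
- Day and month missing: "the imputed day and month will be 01 Jan or the initial treatment date if they have the same year, whichever is later".

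The reason given is that such events are not expected to start before study treatment. A preceding sentence limits the rule: "If adequate information is available, no imputation is needed". What counts as adequate is not defined.

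The notes under Table 5-19 (SAP 5.1.4.2) set the origin for time to onset. Before a touch-up, "the reference date is initial treatment date for TEAEs occurring on or after initial treatment but before touch-up treatment". Afterwards, "the reference date is touch-up treatment date for TEAEs occurring on or after touch-up treatment". Duration uses the same start date: "Duration for TEAEs will be computed as AE end date – AE start date + 1". Both quantities are reported for treatment-related events under the item "Overall summary by duration, time to onset, outcome, and treatment required". Safety Day in Table 6-1 is also counted from the most recent injection, initial or touch-up.

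Protocol 9.1.3 fixes the spacing: "Up to 2 treatment sessions 30 days apart are allowed".

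**The concern.** The SAP treats the touch-up as a separate exposure when it times events, but leaves it out of the rule that supplies the date. The stated reason for the floor, that onset is not expected before study treatment, applies equally to a second injection when the event is known to have followed it.

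Because the floor is only the first of the month or the initial treatment date, an early reaction to re-injection with an unknown onset day can be recorded as a reaction to the first injection several weeks earlier. The same applies to control subjects after their optional treatment. At stake is the accuracy of two descriptive safety summaries, time to onset and duration. No hypothesis test is involved.

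**Working it through.** The plan states no figure on this point, so there is nothing to reproduce. The check applies the two rules together.

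**Inputs from the documents**
- Imputation rule: SAP 6.3.1.
- Time to onset = onset date − reference date + 1, with the reference chosen as above: SAP 5.1.4.2.
- Gap from initial treatment to touch-up: 30 days (Protocol 9.1.3).

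**Assumption:** the lag from touch-up to true onset. The documents give no distribution, so a range is shown.

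**Step 1: logic for a missing day**
- *Onset in the touch-up's month.* The imputed date is the 1st, or the initial treatment date if that falls in the same month. Either is before the touch-up unless the touch-up was on the 1st. The reference becomes the initial injection, which is wrong.
- *Onset in a later month.* The imputed date is the 1st of that month, which is after the touch-up. The reference injection is right.

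**Step 2: worked examples.** Initial treatment 10 March 2016; touch-up 30 days later, 9 April.
- True onset 11 April, recorded as April 2016. True time to onset is 11 April − 9 April + 1 = day 3 after the touch-up. The imputed date is 1 April, giving 1 April − 10 March + 1 = day 23 after the initial injection. Duration is 10 days too long (11 April − 1 April). With the touch-up date in the rule, the imputed date is 9 April, time to onset is day 1 after the touch-up, and duration is 2 days too long.
- True onset 11 May, recorded as May 2016. The imputed date is 1 May, giving day 23 after the touch-up against a true day 33. The day is off, but the injection is right.

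**Step 3: how often.** Take 365 consecutive initial-treatment dates, a touch-up 30 days after each, and every onset lag in the stated range with equal weight. Count the cases where the imputed date precedes the touch-up.

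| True onset after touch-up | Dated before touch-up, day missing |
|---|---|
| 0 to 6 days | 87% |
| uniform over 14 days | 76% |
| uniform over 30 days | 49% |
| uniform over 91 days | 16% |
| uniform over 365 days | 4% |

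In the 0 to 6 day row, the misdated events get a median time to onset of day 17 after the initial injection (IQR 11 to 24, range 1 to 30), against a true day 1 to 7 after the touch-up. Gaps of 28 or 37 days in place of 30 give almost the same shares.

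With day and month both missing, the share is 96% for onset uniform over 30 days and 50% over 365 days.

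**Step 4: what an unconditional change would do.** Add the touch-up date to the comparison for every event. The misdated share for true post-touch-up events with a missing day falls to 0%. However, true pre-touch-up events are now moved to the touch-up: 11% if onset is 0 to 6 days after the initial injection and 49% if it is uniform over the 30 days. Under the current rule this is 0%.

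**The case against.** The strongest reply is that the high percentages belong to the window where onset dates should be best recorded. For 30 days after each treatment subjects keep a safety diary, and there is a telephone call at day 3 (Protocol synopsis; SAP 4.1.1). Adverse events are asked about at every visit after screening (Protocol 11.1.1). Injection site responses are taken from diary dates and tabulated separately for initial and touch-up treatment (SAP Table 5-20). A missing day may therefore be least likely where the rule does most harm. This stands as a limit on size, although the diary does not supply the onset date on the adverse event form.

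The sentence exempting events with adequate information might be read as covering this case. It does not say what is adequate, or what date to use when a touch-up is known to have come first. SAP 6.4 concerns how imputed values appear in listings, so it does not repair the summaries.

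Two stronger readings are tempting and should not be drawn:

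- *Post-touch-up events with an unknown day are generally misdated.* That holds only for onset in the touch-up's calendar month, or if onsets cluster soon after the injection. Follow-up runs up to 12 months, and onset in later months is already timed from the touch-up.
- *The rule inflates late onset and so distorts the picture of delayed reactions, which Protocol 2.2 names as a risk.* The documents set no threshold for delayed onset. With a 30-day gap the misdated value never exceeds day 30. In the second worked example the rule shortens time to onset. With day and month missing and the initial treatment in the same year, the event is placed on the initial treatment date, which is day 1.

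Finally, the visible adverse event tables do not split events by initial and touch-up injection, so the wrong attribution shows only through the day count and the duration.

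**Conclusion.** The inconsistency is real. Followed as written, SAP 6.3.1 dates an event that began after a touch-up, in the touch-up's calendar month and with an unknown day, before the touch-up (unless that was on the 1st). SAP 5.1.4.2 then counts from the initial injection, and duration is too long.

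The share of post-touch-up events with a missing day that are misdated runs from 87% to 16% as the assumed onset window widens from 7 to 91 days. The number of affected events cannot be computed, because neither the touch-up rate nor the frequency of partial dates is in the documents.

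The effect is confined to the time-to-onset and duration summaries of treatment-related events with partial dates, plus any Safety Day derived from those dates. Treated-period incidence is unchanged because the event counts as treatment-emergent under either date. Injection site responses and the primary endpoint do not use this rule. This is a minor point, worth correcting because the correction is cheap.

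**What to change.** Amend both bullets of SAP 6.3.1:

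- Where recorded information places onset on or after the touch-up (for example, the event was first reported after the touch-up visit and not at or before it), impute the later of the first of the month (or 01 Jan if the month is also missing) and the touch-up date, when that date falls in the known month (or year).
- Otherwise, or where a known end date precedes the touch-up, keep the current rule.
- State what counts as adequate information.
- Flag imputed onsets in the time-to-onset table.

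The condition matters. Applied to every event, the change would move 11% to 49% of true pre-touch-up events to the touch-up under the assumptions shown above.

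The cost is a few lines of SAP text and programming. Some misassignment will remain where the recorded information is ambiguous, and the imputed date will still be the earliest one compatible with the record.

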### 6.3.2 Missing/Incomplete AE End Date

[figure not shown]
Imputation of dates with missing day and/or month is only applied to TEAEs. If adequate information is available, no imputation is needed. TEAE end dates with missing day or month will be imputed as following:

- If day and month are missing but year is available, then the imputed day and month will be 31 Dec or the study exit date if they have the same year, whichever is earlier

- If day is missing but the month and year are available, then the imputed day will be the last day of the month or the study exit date if they have the same month and year, whichever is earlier

## **6.4 Imputed Value Listing Conventions**

In general, listings will present the actual partial or missing values rather than the imputed values that may be used in endpoint derivation. In instances where imputed values will be presented, imputed values will be flagged. Actual rules will be fully defined in the table, figure, and data listing specification document.

